## 8 Data entry

All study data from the baseline survey up until the end-of-study survey are entered into an electronic data capture system (ODK) by the investigators and delegated personnel, either directly (in which case these are themselves considered Source data) and/or from a designated primary Source, e.g. paper Case Report Forms (CRF), Blood Smear read out results.

## 9. Coding

Data coding for not standardized data is not applied.

All data in the database is pseudonymized. A study participant identification link log is available at the investigators' site.

## 10 Statistical methods

### 10.1 Demographics

Baseline characteristics (age, gender) will be tabulated. Categorical variables will be presented as count and percentage. Numerical variables will be summarized as median, minimum and maximum. GPS data and maps will be used to present location of compounds and clusters.

### 10.2 Study flow

A study flow chart (e.g. CONSORT flow chart) will be used to present number of volunteers approached for enrolment, enrolled, withdrawn and followed until completion of the study.

### 10.3 Effectiveness of SMC and SMC efficacy decay

*Assessing effectiveness of SMC requires collection of data on:*

- *Coverage (proportion of children reached by the four SMC rounds)*
- *Health Care worker's compliance (proportion of children receiving first dose of SMC under DOT)*
- *Caregiver's compliance (proportion of children receiving correct SMC regimen)*
- *Drug levels (proportion of children with adequate drug level)*

#### SMC treatment coverage

SMC coverage will be assessed through a combination of direct observation of treatment and pharmacological assessments. In arm 1 Directly Observed Treatment (DOT) is applied only on the first day of each SMC round. In arm 2 and 3 DOT is applied for the full three-day course of SMC. DOT includes observation of drug administration and a 15 minutes post-administration observation period. In arms 2 and 3, coverage will be expressed as percentage of the target population receiving at least one dose of SMC, at least two doses of SMC and the full 3-day course of SMC.

The adherence for all study participants will be evaluated based on observed amodiaquine (AQ) and desethylamodiayiune (DEAQ) plasma concentrations 4 days after the last dose of SMC should have been taken (day 7 since the start of the SMC round), as previously described by Ding J. et al. (2020 (viii)).

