### **4 Study objectives**

The specific study objectives are to:

- i) compare SMC effectiveness in children aged 3-59 months as implemented by the national malaria control program and SMC implemented in a research context where all doses are directly observed.
- ii) Evaluate the effectiveness of SMC to reduce malaria infection prevalence in 5-9 year olds

- iii) quantify the infectious reservoir and the contribution of different age groups to transmission with conventional SMC (<5 years) and extended SMC (<10 years)
- iv) determine the impact of drug resistance (by molecular typing of *dhps*, *dhfr*, *pf crt* and *pfmdr1*) and drug absorption on SMC efficacy
- v) understand social barriers and enablers interfering with SMC efficacy and how SMC uptake is related to health equity with special attention to gender inequalities.
- vi) quantify SMC efficacy decay under programmatic conditions and key drivers of this decay.

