## **10.6 Social barriers and enablers**

The qualitative component of the study is designed to understand potential factors that influence SMC uptake and effectiveness.

Throughout the study, data on compliance to SMC treatment guidelines from caregiver and healthcare worker perspectives are collected. Whether first dose was directly observed and whether the full treatment course was administered to the child after each round on SMC is documented. After SMC round 4 a cross-sectional survey will be carried out. For this, individual interviews of caregivers of children targeted or not by the current SMC strategy will be conducted.

Further, within each of the study arms, between 6-8 individuals will be recruited for focus group discussions (FGDs). Community-based field workers will be asked to purposively select individuals for the FGD. Preference will be given for eligible participants that are active in community life and events, and therefore would have had greater exposure to views and experiences of other community members. The selection will pay much attention to gender balance. The FGD will be closed to outside observers, limited only to consenting participants and the fieldworkers conducting the session. Two field workers will conduct the FGD. One field worker will lead the discussion and the other will take notes. The discussion will be recorded for transcription. A semi-structured discussion guide will be used to guide the

discussion. The discussion will last approximately 60 minutes. The recording of the discussion will be used to create a discussion transcript for data analysis.

Key informant interviews (KIIs) and in-depth interviews (IDIs) will be carried out. For the KIIs, participants will be recruited through purposive sampling to include stakeholders within the health system involved in SMC implementation.

The IDIs will be conducted among 5-10 key informants per each of the study arms. These individuals will also be purposively selected using community-based field workers. The aim is to include community leaders, professionals, or residents who have first-hand knowledge about the community. The interviewer will use a semi-structured interview guide to guide the discussion that will last approximately 60 minutes. The interview will be recorded for transcription. The recording of the interview will be used to create a discussion transcript for data analysis.

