10. *Plasma levels of AQ and desethylamodiaquine (DEAQ) after the 4th round of SMC in children aged 3 months-9 years (between arm comparison) [post-SMC round 4].*

A published non-linear mixed-effects pharmacokinetic model will be evaluated for the ability to describe AQ and DEAQ pharmacokinetics in the study population (viii). All quantifiable plasma concentrations available will be used for model evaluation using gold-standard methods. Visual predictive checks and goodness-of-fit plots will be made to assess model performance for participants in which dosing history is observed through DOT. For each study participant 2000 full concentration-time profiles will be simulated, considering participant age and weight, assuming full treatment adherence.

Model-predicted concentrations at the PK sampling time will be determined for each simulation. The optimal cut-off percentile discriminating between adherence and non-adherence was previously determined to be the 20th percentile of the individual simulated concentration-time profiles (71% sensitivity, 80% sensitivity) (viii). Participants with observed plasma concentrations below the individual cut-off percentile will be scored as non-adherent. Coverage will be expressed as percentage of participants scored as non-adherent per treatment arm. Additional analyses will include the percentage of participants with/without any measurable AQ or DEAQ plasma concentrations.

*11. Incidence of clinical malaria captured during passive-case detection (between arm comparison) [[post-SMC round 4]]*

Passive case detection data will be analysed by Poisson regression. The outcome will be the number of cases in each compound. Comparisons will be made between arms 1 and 2 in children aged 3-59 months and between arms 2 and 3 in children aged 5-9 years. There will be a random effect for compound and an offset of the number of children.

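### The plasma adherence score ignores recorded receipt of round 4 and is reported as coverage, so arm 1 merges not being reached with incomplete dosing

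*SAP*

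**What the plan says.** Section 10.3 lists four kinds of data needed to assess SMC effectiveness: coverage (children reached), health worker compliance with observing the first dose, "Caregiver's compliance (proportion of children receiving correct SMC regimen"), and drug levels. They are listed as separate items.

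The same section then gives the plasma rule. Its population is every participant: "The adherence for all study participants will be evaluated based on observed amodiaquine (AQ") and its metabolite DEAQ. The sampling time follows the due date of the last dose, not its recorded receipt: "plasma concentrations 4 days after the last dose of SMC should have been taken (day 7 since the start of the SMC round").

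Section 10.7, endpoint 10, covers children aged 3 months to 9 years. Concentration profiles are simulated for each participant, "considering participant age and weight, assuming full treatment adherence". Then: "Participants with observed plasma concentrations below the individual cut-off percentile will be scored as non-adherent". The summary measure is: "Coverage will be expressed as percentage of participants scored as non-adherent per treatment arm". The share with and without any measurable drug is an additional analysis.

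Three other places bear on this:

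- Section 10.3 expresses coverage by number of doses received for arms 2 and 3 only.
- Section 10.6 says of the data collected: "Whether first dose was directly observed and whether the full treatment course was administered to the child after each round on SMC is documented".
- Objective vi (Section 4) is to "quantify SMC efficacy decay under programmatic conditions and key drivers of this decay". Endpoint 16, which should deliver it, appears in Section 10.7 with no method beneath it.

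**The concern.** The plan names separate steps at which SMC effect can be lost, then fixes a score that cannot tell two of them apart. A targeted child missed in round 4 and a child whose home doses were not all given can both fall below a cut-off built on full adherence. Calling the resulting percentage coverage adds to the confusion: it runs in the opposite direction to coverage, and it is neither the proportion reached in the Section 10.3 list nor the dose-count measure defined for arms 2 and 3.

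This matters most in arm 1, where decay under programmatic conditions arises. If delivery varies while home dosing stays the same, the reported figure moves, and a reader cannot see which step moved it. The two causes call for different responses, and telling them apart is the purpose of objective vi.

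There is also a denominator problem. Children aged 5-9 years receive SMC in arm 3 only, yet endpoint 10 covers ages 3 months to 9 years per arm. Taken literally, untargeted children in arms 1 and 2 are scored against a full-adherence profile and come out non-adherent.

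**Working it through.** **The plan's own plasma figure.** Section 7 states 86.3% power for a Welch t-test on log DEAQ with 120 children per group. Inputs: medians 550 and 400 ng/mL, IQRs 350-850 and 200-700.

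- Difference: ln 550 − ln 400 = 0.318.
- SDs: (ln 850 − ln 350)/1.349 = 0.658 (DOT) and (ln 700 − ln 200)/1.349 = 0.929 (non-DOT).
- Standard error: √((0.658² + 0.929²)/120) = 0.104; noncentrality 0.318/0.104 = 3.07.
- Power, two-sided 5% (alpha is not stated there): 86.3%.

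The figure reproduces and is not in dispute. (The text gives the two SDs in reverse order for DOT and non-DOT; with equal groups this does not affect power.)

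**Effect of ignoring receipt.** Let *u* be the share not reached, *f* the share fully adherent and *p* = 1 − *f* − *u* the share partly dosed. Children not reached are always scored non-adherent.

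- Scored among all = *u* + *p* × sens + *f* × (1 − spec)
- Scored among reached = [*p* × sens + *f* × (1 − spec)] / (1 − *u*)

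Inputs:

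- *f* = 50%. Section 7 anticipates less than 50% complete adherence in arm 1, so this is the bound.
- Sensitivity 71% and specificity 80%. Endpoint 10 gives 71% and 80% but labels both sensitivity, so this reading is an assumption.
- *u* = 5% to 30%, assumed. Section 7 anticipates more than 20% taking no dose but does not say why.

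| Not reached | Among all | Among reached | Gap (points) |
|---|---|---|---|
| 5% | 46.9% | 44.2% | 2.8 |
| 10% | 48.4% | 42.7% | 5.7 |
| 20% | 51.3% | 39.1% | 12.2 |
| 30% | 54.2% | 34.6% | 19.6 |

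At 20%: among all, 0.20 + 0.30 × 0.71 + 0.50 × 0.20 = 0.513; among reached, 0.313/0.80 = 0.391.

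**Sensitivity of the 20% case.**

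- Accuracy figures reversed (80% and 71%): 58.5% against 48.1%, gap 10.4.
- *f* = 40%: 56.4% against 45.5%, gap 10.9.
- 71% taken as average detection over all non-adherent children, no-dose children included: implied detection of partial dosing is (0.71 × 0.50 − 0.20)/0.30 = 51.7%, giving 45.5% against (0.155 + 0.10)/0.80 = 31.9%, gap 13.6.

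**Delivery alone.** Hold incomplete dosing among reached children at 30%. Their score is 0.30 × 0.71 + 0.70 × 0.20 = 35.3%. With nobody missed, the all-participant score is also 35.3%; with 20% missed it is 0.20 + 0.80 × 0.353 = 48.2%. Home dosing has not changed.

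**Untargeted children.** Section 6 expects 1.5 children under 5 and 1.5 aged 5-9 per compound. If both groups were sampled equally, every targeted child were fully adherent, and untargeted children had no amodiaquine from elsewhere, the literal rule would give 0.5 × 20% + 0.5 × 100% = 60% non-adherent in arm 2 and 20% in arm 3.

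**The case against.** Several points on the other side stand.

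- **Label.** A reader might infer that the SAP counts missed delivery as caregiver non-adherence. It does not: caregiver compliance is a separate item in Section 10.3, and the plasma score is called only non-adherent.
- **Separability.** A reader might infer that the drivers cannot be separated. They can, given the receipt records described in Section 10.6. Drug detectability helps, though on its own it does not distinguish not reached from reached but not taken.
- **Purpose of the arm comparison.** Objective i compares SMC as the national programme implements it with fully observed SMC. Failure to reach children is part of programmatic implementation, so a score over all targeted children suits that comparison and respects randomisation. The SAP does not say an arm difference would be attributed to unobserved home doses alone.
- **Meaning of no dose.** Section 7 does not equate taking no dose with not being reached. The first dose is meant to be observed in arm 1, which makes the link plausible, but Section 10.3 treats health worker compliance with that step as something to be measured. Any statement that a fixed share of non-adherent children are delivery failures would rest on that unstated link.
- **Age groups.** Section 2.3 says coverage differences are assessed in the SMC-targeted age groups, and Section 7 sets its sampling targets for arms 1 to 3 in under-fives. Scoring untargeted children is probably not intended.
- **Weight.** Decay is exploratory and plasma level is one of ten secondary endpoints. The primary comparison is unaffected.

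None of this supplies a receipt condition, a dose-count coverage measure for arm 1 or a method for endpoint 16, nor does it justify reporting percent non-adherent as coverage.

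**Conclusion.** The point holds as a fault in a stated rule and in its labelling. Followed as written, Sections 10.3 and 10.7 produce an arm 1 figure that moves with missed delivery as well as with incomplete dosing, under the name of coverage, and leave the split for objective vi unspecified. The excess over the among-reached score is about 3 to 20 points for 5% to 30% not reached, and about 10 to 14 points at 20% across the accuracy and adherence assumptions tried. All of this is illustrative, since the share not reached, the reading of the two accuracy figures and certain detection of unreached children are assumptions. The endpoint 10 age range conflicts with Section 2.3 and needs reconciling. The documents do not support going further, to a claim that caregivers are being blamed or that separation is impossible. The change should be made before the analysis, but it does not threaten the primary endpoint.

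**What to change.** In Section 10.3 and endpoint 10:

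1. Restrict the adherence score to SMC-targeted children: 3-59 months in arms 1 and 2, and 3 months to 9 years in arm 3.
2. Define coverage in every arm as recorded receipt of round 4 in the target population. Keep receipt distinct from whether the first dose was observed, since a child may be reached without being observed.
3. Report, per arm, (a) not reached, (b) reached with concentration below the cut-off, (c) reached with concentration above it. Coverage loss is a/(a+b+c); adherence loss is b/(b+c).
4. Replace the sentence that expresses coverage as percent non-adherent.
5. Keep the all-targeted percentage as the randomised arm 1 against arm 2 comparison in children aged 3-59 months, with the cluster and village terms of outcome 1. Present adherence among reached children as descriptive, because being reached is a post-randomisation event that may differ by arm.
6. Under endpoint 16, state that these quantities are the steps used to describe decay.

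The cost is SAP wording and a cross-tabulation of data Section 10.6 says are recorded, provided those records cover the children with plasma samples. The downside is small: the adherence figure rests on fewer children, about 80% of the arm 1 sample if 20% are not reached.

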## Qualitative data on compliance

*See section 10.6*

### Biomarkers:

Serological analysis of blood samples will be conducted using bead based assays to assess presence of biomarkers for correlates of infection (i.e. proteins associated with inflammation or parasite density (HRP2)). These biomarkers, assessed at individual level will be related to parasite positivity, transmission efficiency etc. as part of exploratory analyses.

## **10.4 Human infectious reservoir**

The human infectious reservoir will be assessed by a combination of direct measurements of transmissibility (assessed in a selection of parasite-positive children aged 5-9 years) and modeling/transmission imputation as described in detail in section 10.7 endpoint 12.

## **10.5 Drug resistance**

Nucleic acids will be extracted with commercial kits [Qiagen] from blood samples collected on filter paper. Three dual-labelled probes were designed to detect three crt genotypes at codons 72-76 (encoding Cys-Val-Met-Asn-Lys [CVMNK], CVIET, and SVMNT).

## **10.6 Social barriers and enablers**

The qualitative component of the study is designed to understand potential factors that influence SMC uptake and effectiveness.

Throughout the study, data on compliance to SMC treatment guidelines from caregiver and healthcare worker perspectives are collected. Whether first dose was directly observed and whether the full treatment course was administered to the child after each round on SMC is documented. After SMC round 4 a cross-sectional survey will be carried out. For this, individual interviews of caregivers of children targeted or not by the current SMC strategy will be conducted.

Further, within each of the study arms, between 6-8 individuals will be recruited for focus group discussions (FGDs). Community-based field workers will be asked to purposively select individuals for the FGD. Preference will be given for eligible participants that are active in community life and events, and therefore would have had greater exposure to views and experiences of other community members. The selection will pay much attention to gender balance. The FGD will be closed to outside observers, limited only to consenting participants and the fieldworkers conducting the session. Two field workers will conduct the FGD. One field worker will lead the discussion and the other will take notes. The discussion will be recorded for transcription. A semi-structured discussion guide will be used to guide the

discussion. The discussion will last approximately 60 minutes. The recording of the discussion will be used to create a discussion transcript for data analysis.

Key informant interviews (KIIs) and in-depth interviews (IDIs) will be carried out. For the KIIs, participants will be recruited through purposive sampling to include stakeholders within the health system involved in SMC implementation.

The IDIs will be conducted among 5-10 key informants per each of the study arms. These individuals will also be purposively selected using community-based field workers. The aim is to include community leaders, professionals, or residents who have first-hand knowledge about the community. The interviewer will use a semi-structured interview guide to guide the discussion that will last approximately 60 minutes. The interview will be recorded for transcription. The recording of the interview will be used to create a discussion transcript for data analysis.

## 10.7 Analysing data and reporting results

When analysing data based on age, participants' age at time of the first round of SMC is used. If a child received SMC because he/she was <5 years at the time of SMC but turns 5 prior to the last survey, the age at the moment of SMC round 1 is used since this dictated the intervention.

### Primary endpoint

1. *Parasite prevalence by quantitative PCR (qPCR) at the end of the transmission season in age groups targeted by seasonal malaria chemoprevention. [end-of-study survey].*

This endpoint will be compared between arms 1 and 2 (in children aged 3-59 months) and arms 2 and arm 3 (in children aged 5 years--9 years). Parasite prevalence by qPCR will be used as binary variable with all parasite densities above 100 parasites/mL (0.1 parasite/ $\mu$ L) being classified as parasite positive. Parasite prevalence is compared between arms by logistic regression; models will account for clustering by including cluster as a random intercept and village as a fixed effect.

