### 2.3 Design & intervention

The study is designed to evaluate SMC effectiveness and consists of three interventional study arms, with the first arm receiving an intervention that is implemented as part of routine control.

Study arm 1:	SMC in children under the age of 5 years, implemented by the Ministry of Health (MoH) without directly observed treatment for the full course of SMC
Study arm 2:	SMC in children under the age of 5 years, with directly observed treatment for the full course of SMC
Study arm 3:	SMC in children under the age of 10 years, with directly observed treatment for the full course of SMC

SMC consists of SP and AQ administered daily for three days. SP is given on the first SMC day only while AQ is given daily over three days. In total 4 rounds of SMC will be conducted during the peak malaria transmission season from July to October, separated by approx. 30 days.

Each study arm contains 62 clusters; each cluster consists of 3 compounds where each compound has at least one child aged 3-59 months and one child aged 5-9 years. (186 compounds per arm; 558 compounds in total). Differences in SMC coverage and efficacy will be determined in the SMC-targeted age groups. In contrast, all age groups will take part in the evaluation of the study to assess the impact of the intervention on the infectious reservoir in the community and compare parasite carriage in targeted and untargeted populations. To detect possible behavioural contamination and differences in SMC uptake or adherence in study arm 1 compared to what would be observed if there would be no

study team present, a single cross-sectional survey 7 days after the last (4th) round of SMC coverage is assessed outside the study area (2-5 kilometres from the nearest enrolled study compound) by questionnaire and samples to determine plasma levels of SMC drugs and parasite carriage by qPCR. Plasma levels of SMCR drugs are used as the most definitive evidence of differences in SMC uptake/adherence.

Scheduled surveys and scheduled or unscheduled sampling timepoints will take place in each arm; these surveys are designed and timed for several outcome measures and include:

- i) a survey prior to first SMC roll-out (performed in all compounds).
- ii) mid-study surveys 3, 4 and 5 weeks after the last SMC roll out (each compound will participate in one of these surveys).
- iii) end-of-study survey up to 10 weeks after last SMC roll out (performed in all compounds).

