### **3 Randomization**

The unit of randomization will be the cluster; each cluster comprises of 3 compounds. Clusters are randomly allocated to one of the three study arms by a computer generated algorithm and stratified by village. Stratification by village was to account for spatial differences in malaria exposure, distance from health facilities, and treatment seeking behavior. In total, 185 clusters were randomized.

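### The primary model is valid but adjusts only for village; age at round 1, and the child's baseline parasite status if measured, should be added for a modest gain

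*SAP*

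**What the plan says.** SAP section 10.7, Primary endpoint: "Parasite prevalence is compared between arms by logistic regression", and "models will account for clustering by including cluster as a random intercept and village as a fixed effect". The two contrasts are each confined to one age band: "This endpoint will be compared between arms 1 and 2 (in children aged 3-59 months) and arms 2 and arm 3", the second contrast being in children aged 5–9 years.

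Section 3 explains the village term. Clusters were allocated "by a computer generated algorithm and stratified by village", and "Stratification by village was to account for spatial differences in malaria exposure" as well as distance from health facilities and treatment seeking.

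Two other places bear on what could be adjusted for:
- Section 2.3 schedules "a survey prior to first SMC roll-out (performed in all compounds"). It does not say what that survey measures.
- Section 10.1 states that "Baseline characteristics (age, gender) will be tabulated", and section 10.7 that "When analysing data based on age, participants' age at time of the first round of SMC is used". So age at round 1 is available, but the SAP uses it only to describe participants and to assign age groups.

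Secondary outcomes 3 to 9 refer back to the method of outcome 1. Outcomes 3 and 8 cover all age groups, and outcome 4 names no age group.

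**The concern.** Adjusting for a prognostic baseline variable usually buys some precision and removes the effect of chance imbalance in that variable. Village is in the model, but it cannot capture differences between three-compound clusters, or between children, inside a village. The sizing itself allows for variation between clusters (coefficient of variation 0.3).

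Age is the clearer omission because the SAP shows that it is held. Within the primary comparisons the age band limits how much it can matter. In the all-age outcomes that inherit the model there is no such limit, and no age term is specified.

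At stake are some avoidable width in the confidence intervals and some exposure to imbalance within villages. The validity of the tests is not at stake.

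**Working it through.** **Inputs from SAP sections 6 and 7.** Prevalence 40% v 25% (older children) and 16% v 7% (under 5); c = 55 clusters per arm; m = 4.5 children per cluster and age group (section 6), or 6 (the section 7 calculation); k = 0.3; alpha 0.05, taken as two-sided. The SAP gives no baseline–outcome association, so every gain below rests on an assumption.

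**The plan's own figure.** With w = [p0(1−p0) + p1(1−p1)]/m and b = k²(p0² + p1²), λ = √[(c−1)(p0−p1)²/(w+b)] and power = Φ(λ − 1.96).
- 40% v 25%, m = 6: w = 0.0713, b = 0.0200, λ = 3.65, power 95.4%. The stated 87% is not reproduced. With m = 4 the result is 87.2%. This is a separate matter.
- 40% v 25%, m = 4.5: w = 0.0950, b = 0.0200, λ = 3.25, power 90.1%.
- 16% v 7%, m = 4.5: w = 0.0443, b = 0.0027, λ = 3.05, power 86.2%.

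**Ceiling for a cluster-level covariate.** The between-cluster share b/(w+b) is 17% for 40% v 25% and 6% for 16% v 7%. Explaining all of it would lift power only to 94.7% and 88.1%. A cluster prevalence from 4.5 children is also a noisy covariate. Its reliability, (0.3p)²/[(0.3p)² + p(1−p)/4.5], is 0.09 at an assumed baseline prevalence of 20% and 0.21 at 40%. In simulation, cluster prevalence plus age changed information by −0.4% to 2.2% (16% v 7%) and −0.5% to 5.5% (40% v 25%).

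**The child's own baseline status plus age.** Simulating the logistic analysis with assumed odds ratios of 1.5–4 for baseline status and 1.2–1.6 per SD of age gave about 0–7% more information for 16% v 7% and 0–12% for 40% v 25%. A closed-form check agrees. Let R² = 1 − ΣE[p(x)(1−p(x))]/Σp(1−p), summed over arms, and information ratio = (w+b)/[w(1−R²)+b]. At an assumed baseline prevalence of 30%:

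| OR baseline / OR age | 16% v 7% | 40% v 25% |
|---|---|---|
| 1.5 / 1.2 | +0.8% | +1.2% |
| 2 / 1.4 | +2.5% | +3.8% |
| 4 / 1.6 | +8.0% | +11.3% |

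In power terms the upper ends are:
- 16% v 7%: 3.05 × √1.07 = 3.15, power 88.4% (from 86.2%).
- 40% v 25%: 3.25 × √1.12 = 3.44, power 93.0% (from 90.1%).

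Most of the assumed range lies well below these.

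**Chance imbalance.** At an assumed 30% baseline prevalence, the variance of a cluster mean is 0.21/4.5 + (0.3 × 0.3)² = 0.0548. The 1-in-20 difference between arms is 1.96 × √(2 × 0.0548/55) = 8.7 percentage points, before village stratification reduces it. With a baseline–outcome correlation r, the under-5 estimate shifts by r × (0.319/0.458) × 8.7 points, where 0.319 = √(0.115 × 0.885) and 0.458 = √(0.3 × 0.7). That is 0.6 points at r = 0.1 and 1.8 at r = 0.3, against a planned difference of 9 points.

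**The case against.** The strongest reply is that nothing here is wrong. The model handles clustering, contains the stratifier, and is valid under randomisation. Residual imbalance is already reflected in the confidence interval. That stands, and it makes this a recommendation for improvement.

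The SAP also never says that the pre-SMC survey measures parasites. That stands too, and the baseline-status term must be conditional on it. Nor can one infer that the survey's results go unused: the infectious-reservoir analysis (outcome 13) draws on gametocyte density at whichever timepoints are relevant, which may include this one.

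A reader might take 16% v 40% as proof that age is strongly prognostic. It is not. The first figure is for under-fives with SMC and the second for older children without it, so age and treatment are mixed. The contrast also lies between bands, while each primary comparison stays inside one.

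Finally, under-5 events are few: 55 × 4.5 × (0.16 + 0.07) ≈ 57 over both arms, with village fixed effects already in the model. This argues for few added terms and against a cluster-prevalence term. It does not argue against age and, where measured, the child's own baseline status.

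**Conclusion.** The point holds as a modest improvement to a valid analysis. The expected gain is about 0–7% more information for 16% v 7% and 0–12% for 40% v 25%, or about 0–2 power points and nearly 3 at the extreme in older children. To this is added correction of chance imbalance within villages. The size rests on assumed odds ratios and an assumed baseline prevalence; the simulations omit village effects.

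A reader might infer much more: correlations of 0.3–0.5 would cut variance by 9–25%, which equals 10–33% more clusters (1/0.91 and 1/0.75) and up to 94% power in the under-fives. The documents give no such correlations, and they are implausible for this outcome. With 11.5% mean outcome prevalence and 30% baseline prevalence, a correlation of 0.3 puts outcome risk at 26.1% v 5.2%, an odds ratio of about 6. A correlation of 0.5 puts it at 35.9% v 1.1%, an odds ratio above 50.

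Nor is the change free. The odds ratio becomes conditional on the covariates, and missing baseline data need a rule.

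**What to change.** In section 10.7, before arm-labelled results are examined:
- Add age at round 1, continuous, to the primary model and to the models that refer back to it. For the all-age outcomes 3 and 8, model age flexibly (for example with a spline), since a straight line over all ages is unlikely to fit. Apply the same to outcome 4 if it is analysed across age groups.
- If the pre-SMC survey measured parasites, add the child's own baseline status with a missing-indicator, and tabulate baseline prevalence by arm. Do not add cluster baseline prevalence.
- Keep the model with village and cluster only as a sensitivity analysis, and name it as the fallback if the adjusted model does not converge.
- Report a standardised prevalence difference with its confidence interval beside the odds ratio, because the trial was sized on prevalence and the adjusted odds ratio is covariate-conditional.

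The cost is SAP wording, one missing-data rule and one extra reported estimate. If the survey took parasite samples, no new data are needed; if not, only the age term applies.
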